5.4. Exposures / interventions

Silimed Indústria de Implantes Ltda

[name]

[contact] **[contact]

www.silimed.com.br • [contact] • facebook: silimed international/brasil

5.4.1. Interventions of major interest.

Silicone Gel Implant with Polyurethane Foam-Coated Surface

Composed of a single silicone elastomer shell, mechanically resistant and coated with polyurethane foam. Contains a defined volume of high performance transparent silicone gel (HSC) developed so that its shape and consistency provide a natural breast appearance.

The shell with low bleed treatment are a contribution to the reduction of the transudation of silicone by osmosis, by the barrier of the elastomer shell, where part of the thickness of the shell is formed by an inner layer of elastomer especially impermeable to the silicone oils.

There is evidence that the implant with the polyurethane foam-coated surface presents a lower rate of capsular contracture when compared to a smooth surface. [11-13] The polyurethane coating allows a better interaction between the implant and the tissue around it. The well-irregular surface of the polyurethane foam disadvantages the formation of the linear fibrotic capsule in favor of the multiplanar formation of the collagen fibrils. The formation of microcapsules around the polyurethane particles causes the contraction force to cease to have a single orientation, having multiple vectors, this force tends to cancel out, reducing the capsular contracture. [11]

It is up to the physician to select the appropriate size and type of fixation to meet the clinical and aesthetic requirements of each case. They are all supplied sterile and intended for single use. The package should only be opened inside the operating room and supplied with an auxiliary glove for implantation.

Silicone Gel Implant with Textured Surface

Composed of a single silicone elastomer shell, mechanically resistant, with a textured surface. Contains a defined volume of high performance transparent silicone gel (HSC) developed so that its shape and consistency provide a natural breast appearance.

The shell with low bleed treatment are a contribution to the reduction of the transudation of silicone by osmosis, by the barrier of the elastomer membrane, where part of the thickness of the membrane is formed by an inner layer of elastomer especially impermeable to the silicone oils. The textured surface is effective in reducing the occurrence of capsular contracture when compared to the smooth surface, [11-13] by allying with the low bleed shell in the greatest capacity to prevent this clinical condition.

It is up to the physician to select the appropriate size and type of fixation to meet the clinical

Silimed Indústria de Implantes Ltda

[name]

[contact] [contact]

www.silimed.com.br • [contact] • facebook: silimed international/brasil

and aesthetic requirements of each case. They are all supplied sterile and intended for single use. The package should only be opened inside the surgical center, also containing auxiliary glove for implantation.

5.4.2. Descriptive characteristics or that could interfere in the prognosis.

The rationale for conducting a randomized clinical trial is to create "comparable" groups (e.g. standard group / comparison vs. new intervention) such that the effects observed at the end of follow-up can be attributed to intervention. For this purpose, it is necessary to verify, at the beginning of the follow-up, the characteristics that can lead to confounding. This procedure is also performed in non-randomized trials, and additionally these same characteristics may serve as elements to be adjusted, for example in group formation, where the estimation of event rates could be biased due to confounding (e.g. at some point the groups could be considered "non-comparable" given differences in initial characteristics requiring adjustments).

These characteristics will be grouped as follows: (a) clinical characteristics, (b) characteristics related to surgical procedures and wound care, and (c) characteristics related to the intervention / implants.

Examples of clinical characteristics (but not restricted to): age, weight, body mass index, marital status, ethnicity (skin color), instruction / education, comorbidities (e.g. Arterial hypertension, Diabetes Mellitus, Allergies, etc), use of medications, etc.

Elements related to surgery and surgical wound care (but not restricted to): implant placement technique (subglandular, submuscular, others), type of incision (periareolar, submammary, in previous procedure scar, others), size of the incision etc.

Examples of implant-related (but not restricted to) characteristics: texture, implant type, implant size, etc.

5.5. Primary Outcomes

Primary outcomes will be the adverse events of the participants. Below is a section on the safety, monitoring, and classification of adverse events. The project foresees the classification of **Silimed Indústria de Implantes Ltda**

adverse events according to severity, intensity, causality, type (tissue-related, aesthetic or implant-related events) and according to the course of action for the solution of the event (e.g. unnecessary additional treatment, additional surgical treatment, surgical treatment without explantation and surgical treatment with explantation).

The events related to the tissue are the events that can occur following any breast surgery. Aesthetic events are primarily aesthetic and related to the presence of the implant (e.g., ripples, wrinkles, etc.). Events related to the implant are those that are specifically assigned to the presence of the implant (e.g., capsular contracture, implant rupture, etc.).

The adverse events can be defined as any medical event, yet the literature points to some occurrences as more frequent or as expected, since they are events observed in previous studies and their incidence has already been estimated in these studies. Below is a list of events recorded in previous studies that are considered as expected adverse events:

- Anesthesia: loss of local sensitivity, booth for pain and other sensations, usually reported by the patient during the medical evaluation.
- Asymmetry: after implantation, the breasts do not look identical or have a dissimilar appearance when both sides of a central line are compared for shape, size, level, or location.
- Tissue atrophy: thinning or shrinking of the skin, usually detected on inspection.
- Calcification of the capsule: deposits of calcium salts in the capsule or as a thin layer around the implant. Calcification may be local or diffuse and is usually asymptomatic, occasionally detected when an image of the chest (e.g. radiography or MRI) is performed for investigation of other health conditions.
- Cyst (requiring biopsy or removal): Cyst is a closed structure, such as a sac or bladder, formed in tissues, containing fluid or semi-fluid in its interior. May or may not have a calcified capsule. It can be identified by physical examination and medical evaluation if it is superficial, or by imaging tests (e.g. radiography or tomography)
- Capsular contracture (Baker's classification - check below): Capsular contracture occurs when the collagen fiber capsule shrinks, tightens and compresses the breast implant. Its identification and classification can be conducted during the medical evaluation by inspection and physical examination. [31,32]
- Wound dehiscence: opening of an incision that has been surgically closed. Identified during medical inspection and evaluation.

Silimed Indústria de Implantes Ltda

[name]

[contact] [contact]

www.silimed.com.br • [contact] • facebook: silimed international/brasil

- Delay in surgical wound healing: Too long progression in wound healing; The surgical wound does not heal normally or takes longer than expected. Defined as requiring additional care (e.g. dressings or additional treatment) after 7 days of implantation.
- Displacement: movement of the implant from the original location or appropriate position, due to gravity, capsular contracture, muscle traction, healing forces or implant weight. It can be detected on inspection or physical examination.
- Breast pain: pain in the scar, in the breast or adjacent structures, and may be irradiation of a breast pain.
- Wrinkle: Unnatural nodular appearance that may occur on the side of the breast or underneath it. It can be identified by inspection and clinical evaluation.
- Extrusion: displacement of the implant through a rupture of the skin or through the surgical wound with the tendency of the original implant to exit the implant.
- Galactorrhea: spontaneous flow of milk from the breast, not associated with gestation and delivery, or breastfeeding. It can be both informed by the patient and visualized during inspection and medical evaluation.
- Hematoma: rupture of blood vessels followed by collection of blood and possibly clot formation may occur in structures adjacent to the implant, especially soon after implantation. Hematoma is spontaneously absorbed. They may require surgical drainage because of their size, location, severity or because of possible undesirable clinical consequences. The need for drainage will be assessed clinically on a case-by-case basis. Identified during medical evaluation and physical examination, occasionally identified through imaging tests such as ultrasound.
- Hypoesthesia: reduced local sensitivity, both for pain and other sensations, usually reported by the patient during the physical examination.
- Inflammation or irritation: response of the body to an external infection or aggression, which is characterized by redness, edema, heat or pain. Detected through inspection and physical examination.
- Lymphedema or lymphadenopathy: enlargement and engorgement of the lymph node (s), usually leading to edema resulting from lymph stasis. It can be identified on physical examination, especially if compared to a contralateral structure.
- Implant malposition: occurs when the implant is poorly positioned in the initial surgery. If implantation was considered adequate first and there was displacement, the event should be recorded as displacement (see above).

Silimed Indústria de Implantes Ltda

[name]

[contact] [contact]

www.silimed.com.br • [contact] • facebook: silimed international/brasil

- Need for surgical removal of a capsule or scar (unacceptable scarring): The location of the incision or envelope may progress to an aesthetic result that does not look like healthy or expected skin.
- Need to remove the implant: removal of the implant will be considered a consequence, i.e. an additional therapy of a previous adverse event. It will not be considered an adverse event if it is performed only and exclusively at the request of the patient.
- Necrosis: cell death of tissues. Necrosis has several classifications according to the pathogenesis. It can usually be clinically identified by inspection because of the typical appearance or odor, or additional vascular findings.
- Ripple: The surface of the breast presents with ripples. It can be identified by physical examination.
- Palpability or visibility of the implant: the implant becomes visible or perceptible to the touch.
- Paresthesia or hyperesthesia of the breast or nipples: abnormal sensation (e.g. numbness or itching) or acute sensations with no apparent cause such as pain, heat, cold or touch. Usually identified when informed by the patient during physical examination.
- Ptosis: Flaccidity and sagging of the breast, usually identifiable by inspection.
- Rash: a rash or efflorescence on the skin.
- Implant rupture: a hole or tear in the implant housing that allows the implant filling material, its contents, to escape from the housing. The ruptures may be intracapsular (within the capsule of the scar tissue surrounding the implant) or extracapsular (outside the scar tissue around the implant).
- Seroma: Similar to a hematoma, it occurs when the aqueous portion of blood is collected around a surgical incision or around a breast implant. Depending on its size and extent it may be identified on the physical examination, and additionally on the image (e.g. tomography, MR or US).

In case of reoperation, the frequencies of the reasons that led to reoperation within each initial indication will be studied, mainly if the reoperation was motivated by cosmetic / cosmetic reasons or not. In case of explantation, the following aspects will be investigated: (1) indication for explantation, (2) which adverse events were involved that culminated in the indication of explantation, (3) clinically relevant observations at the time of explantation (e.g. appearance of the capsule, gross defects, general conditions of the implants, etc), (4) if capsulectomy was performed, (5) discoloration and

Silimed Indústria de Implantes Ltda

[name]

[contact] [contact]

www.silimed.com.br • [contact] • facebook: silimed international/brasil

amount of extrusion content, (6) presence and extent of rupture, seroma, hematoma, inflammation or ALCL, (7) condition and appearance of the capsule. Silimed® will gather the information available from each explanation and will perform the procedures of analysis of removed implants.

For some selected adverse events (most frequent), the risk of recurrence of the same adjusted / stratified events by the type of treatment of the first event will be estimated. The most frequent events that need treatment are expected to be capsular contracture. The capsular contractures will be classified according to Baker's classification that considers whether the implant was for primary augmentation or for reconstruction. [31,32]

Table. Baker's classification for capsular contracture after breast augmentation surgery.

Class 1	Absolutely natural breasts. No one notices that there was an increase of the breasts.
Class 2	Minimal contraction. It is possible to note that surgery was performed, but patient does not present complaints.
Class 3	Moderate contracture: Patient notices hardening.
Class 4	Evident contracture. Apparent only by observation.

5.5.1. Monitoring of adverse events

During the study (which begins when free and informed consent is signed), the investigator should monitor each participant for any occurrence of any adverse event (AE). An adverse event (AE) is defined as any unfavorable medical occurrence, unintentional harm, injury or undesirable clinical signs (including abnormal laboratory findings) in research participants, whether or not related to the medical device under investigation. Events related to the procedures involved (any procedure in the clinical investigation protocol) are also considered as AE. [33] All events that occur after the signing of the WICF must be registered in the proper AE form.

An AE may be a signal, a symptom, a complementary test with an abnormal or unexpected result for that participant. Any worsening of pre-existing conditions or new disease or syndrome should be recorded on an AE form. The nature of AE, starting date, duration, intensity, need for treatment, classification of causality, possible alternative etiologies, AE outcome, etc. along with the codifications of affected event and system are required information on the forms of AE for a better understanding

Silimed Indústria de Implantes Ltda

[name]

[contact] [contact]

www.silimed.com.br • [contact] • facebook: silimed international/brasil

and interpretation of the events.

The AEs should be actively investigated, i.e. the investigator should inquire into all AE assessments that have occurred in the period since the previous evaluation, and the investigator should not expect the participant to spontaneously report any such event. The active approach is particularly true for the expected AEs. For this purpose, a specific form for registration, follow-up and closure of each adverse event in this investigation will be developed. Each AE must be completed in the form. This means that a participant may have one or more AE forms completed in a same medical evaluation, corresponding to distinct events that may have different classifications, follow-ups, and behaviors. If the participant seeks medical assistance between scheduled visits due to an AE, the investigator must proceed with appropriate medical care, record the AE on a new form (in the case of a new AE) or complete data on an AE form in progress (in the case of one not yet closed). Therefore, clinical follow-up, registration on the AE forms should not be restricted to scheduled visits. When, during the visits scheduled for the period under evaluation, no AE has occurred, the non-occurrence of AE (negative notification) should be recorded.

Every new AE record or update of an AE in progress must be updated in the database within 3 business days (except those AEs classified as severe that should be reported / updated within 24 hours), even if the event still requires monitoring and the form still needs to be updated for later closure. The investigator will follow all AEs until clinical resolution. At the end of the follow-up, the form and database should be updated one last time for information on how EA has progressed and how it has been resolved.

Some codifications will be used in the AE record for regulatory and comparison purposes. The nomenclature of AE will be according to the MedDRA dictionary (<https://www.meddra.org/how-to-use/support-documentation/portuguese>).

All AEs should be classified according to intensity as described in the qualifying intensity gradation for health conditions (WHO) [33]:

Grade 1 (Light):	A problem is present less than 25% of the time, with an intensity that a person can tolerate and that rarely occurs in the last 30 days.
Grade 2 (Moderate):	It means that a problem that is present less than 50% of the time, with an intensity that interferes in the day to day of people and that happens occasionally in the last 30 days.
Grade 3 (Severe):	It means that a problem that is present in more than 50% of the time, with an intensity that partially alters the day-to-day of people and that happens frequently in the last 30 days.

Silimed Indústria de Implantes Ltda

[name]

[contact] [contact]

www.silimed.com.br • [contact] • facebook: silimed international/brasil

Grade 4 (Complete impairment):	It means that a problem that is present in more than 95% of the time, with an intensity that completely changes the person's day-to-day life and that occurs every day in the last 30 days.
Not specified	It means that there is not enough information to specify the intensity.
Not specified	It means that it is inappropriate to use a gradation (e.g., menstrual functions).

The investigator will use the following WHO-UMC criteria to classify the AE for causality by always having breast implants as the cause of interest [33]:

Certain / Definite:	Event or alteration (abnormal) in a laboratory examination with a plausible temporal relation to the administration of the intervention; It cannot be explained by disease or other intervention or medication; Response to discontinuation or plausible withdrawal (pharmacologically, pathologically); An event defined pharmacologically or phenomenologically (i.e., an objective and specific disorder or a pharmacologically recognized phenomenon); Satisfactory re-exposure, if necessary.
Likely:	Event or abnormal (abnormal) examination in a laboratory with a reasonable temporal relation to the administration of the intervention; Unlikely to be attributed to a disease or other intervention, medicine; Response to discontinuation or clinically reasonable withdrawal; Reexamination not required.
Possible:	Event or alteration (abnormal) in a laboratory examination with a reasonable temporal relation to the administration of the intervention; It can also be explained by illness or other interventions, medications; Information about withdrawal or discontinuation of treatment may be lacking or obscure.
Unlikely:	Event or alteration (abnormal) in laboratory examination that in relation to the moment of administration of the intervention makes an unlikely relationship (but not impossible); Sickness or other treatments subsidize plausible explanations.
Conditional / Unclassified	Event or alteration (abnormal) in laboratory examination; More data is needed for an appropriate assessment, or;

Silimed Indústria de Implantes Ltda

[name]

[contact] [contact]

www.silimed.com.br • [contact] • facebook: silimed international/brasil

	Additional data under investigation.
Not accessible or unclassifiable	The narrative of the report suggests an adverse reaction; It cannot be classified because the information is insufficient or contradictory; Data cannot be supplemented or verified.

Events should be considered serious adverse events (SAE) when they result in any of the following outcomes:

- a) death;
- b) potentially fatal adverse event (one which, in the notifier's opinion, puts the individual at immediate risk of death due to the happened adverse event);
- c) disability / persistent or significant disability;
- d) requires hospitalization of the patient or prolongs hospitalization;
- e) congenital anomaly or birth defect;
- f) any suspicion of transmission of infectious agent by means of a medical device;
- g) clinically significant event.

SAEs should also be considered to be deficiencies in devices that could have led to a serious adverse event if (a) appropriate measures had not been taken or (b) the intervention had not been done or (c) if circumstances had been less favorable. These are addressed under the system for reporting serious adverse events.

Finally, when a planned hospitalization occurs for a pre-existing condition, or a procedure required by the Clinical Investigation Plan, without a serious deterioration, is not considered a serious adverse event.

All SAE events must be registered and notified to the sponsor within 24 hours. Unexpected SAEs classified as possible, probable or defined should be notified to the IRB/IEC and ANVISA by the sponsor. All events will be included in a periodic report for ANVISA and IRB/IEC system.

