4.1. Primary Outcomes

- Estimate the known short-term and long-term risk / adverse event rate for each of the two types of implants of the brand Silimed®.
- Estimate the unexpected short-term and long-term risk / adverse event rate for each of the two types of implants of the brand Silimed®.

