5.3. Study Participants

Participants will be selected consecutively from attendance at participating center, conducted within the recruitment period. The recruitment period will last until the planned minimum sample number is reached, unless the project is interrupted for security reasons. Study participants will be invited to participate in the first medical evaluation after they have performed the implantation

Silimed Indústria de Implantes Ltda

[name]

[contact] [contact]

www.silimed.com.br • [contact] • facebook: silimed international/brasil

procedure and the eligibility criteria described below should be applied.

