5.3.1. Inclusion Criteria

Inclusion criteria: (1) provide free informed consent, (2) female at birth, (3) 18 years or older, (4) have received breast implant(s) for indication of primary augmentation up to 14 days prior, (5) have received breast implants with a textured surface or breast implant with a polyurethane foam-coated surface of the brand Silimed®, (6) ability to comply with the protocol for the entire follow-up time.

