6.3. Eligibility evaluation

This clinical evaluation will consist of two steps, and will occur only after the signing of the ICF. In the first one will be collected personal information about each participant, such as name and address, besides the clinical evaluation, in which the anamnesis and the standard physical examination will be performed on all participants. In the anamnesis, questions will be asked regarding the criteria

Silimed Indústria de Implantes Ltda

[name]

[contact] [contact]

www.silimed.com.br • [contact] • facebook: silimed international/brasil

of inclusion and exclusion in the study, such as previous history of diseases and use of medications.

The physical examination will collect information on weight, height, vital signs, axillary temperature, orientation / lucidity / cooperation, skin ectoscopy, breast evaluation, physical examination of the abdomen, lung and heart, tone / force / gait observation, and any other relevant observation. Other exams may be performed, at the discretion of the study physicians, whenever they are considered necessary, or consult specialists. In case the participant does not meet the eligibility criteria for causes identified in the medical appointment, they will be sent to a specialized medical service.

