6.4. Study Procedures for Visits and Contacts

6.4.1. General summary of the study per visit

Visit 1 / Inclusion (up to 14 days post-surgery)	Visit 2 (60 days post-surgery)	Visit 3 (180 days post-surgery)	Visit 4 (1 year post-surgery)	Visit 5 (2 years post-surgery)	Visit 6 (3 years post-surgery)	Visit 7 (4 years post-surgery)	Visit 8 (5 years post-surgery)	Visit 9 (6 years post-surgery)	Visit 10 (7 years post-surgery)	Visit 11 (8 years post-surgery)	Visit 12 (9 years post-surgery)	Visit 13/Final Visit	
Approach (Reception)	x												
Application of ICF	x												
Clinical Evaluation	x	x	x	x	x	x	x	x	x	x	x	x	x

Silimed Indústria de Implantes Ltda

[name]

[contact] **[contact]

www.silimed.com.br • [contact] • facebook: silimed international/brasil

n																		
Evaluation of adverse events and concurrent medications	x	x	x	x		x		x		x		x		x		x		x
Application of the quality of life and patient satisfaction and evaluator questionnairenaire	x		x	x		x		x		x		x		x		x		x
Contact by phone or other media (retention, orientation, etc.)					x	x	x	x	x	x	x	x	x	x	x	x	x	
Scheduling of the	x	x	x	x		x		x		x		x		x		x		x

Silimed Indústria de Implantes Ltda

[name]

[contact] **[contact]

www.silimed.com.br • [contact] • facebook: silimed international/brasil

next visit																					
------------	--	--	--	--	--	--	--	--	--	--	--	--	--	--	--	--	--	--	--	--	--

6.4.2. Clinical files (CRF) per visit and visit windows.

Visit 1: up to 14 days after implantation	ICF FORM 01 - Identification of participants FORM 02 - Inclusion and Exclusion Criteria FORM 03 - Date of Visit / Surgery FORM 05 - Socio-demographic data FORM 06 - Vital Signs FORM 07 - Surgical Procedures FORM 08 - Rosenberg self-esteem scale and patient satisfaction FORM 09 - Evaluator's satisfaction regarding aesthetic outcome FORM 10 - BEQ - Brazil FORM 11 - Questions
Visit 2: 60 days after implantation (window of + or - 30 days)	FORM 04 - Date of visit FORM 08 - Rosenberg self-esteem scale and patient satisfaction FORM 09 - Evaluator's satisfaction regarding the aesthetic result FORM 10 - BEQ - Brazil FORM 11 - Questions

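### Short-term risk is a primary objective, but no text requires a record of a complication that begins and resolves between surgery and consent

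*Combined protocol and SAP*

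**What the plan says.** Section 4.1 sets as a primary aim: "Estimate the known short-term and long-term risk / adverse event rate for each of the two types of implants". A parallel aim covers unexpected events.

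Entry comes after surgery. Section 5.3: "Study participants will be invited to participate in the first medical evaluation after they have performed the implantation". Inclusion criterion 4 in Section 5.3.1 allows women who "have received breast implant(s) for indication of primary augmentation up to 14 days prior".

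Section 5.5.1 states that the study begins when consent is signed, and sets the recording duty from that point: "All events that occur after the signing of the WICF must be registered in the proper AE form". It also asks for active inquiry: "the investigator should inquire into all AE assessments that have occurred in the period since the previous evaluation".

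At Visit 1, the table in Section 6.4.1 ticks the row "Evaluation of adverse events and concurrent medications". Section 6.4.2 lists a clinical history and a full examination among the Visit 1 procedures, but no adverse event review; its lists for Visits 2 to 12 do include one. The adverse event diary is first handed out at Visit 1. Section 6.3 describes the history-taking by reference to eligibility: "In the anamnesis, questions will be asked regarding the criteria".

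Among the expected events, Section 5.5 says that hematoma may occur "especially soon after implantation. Hematoma is spontaneously absorbed", and adds that some hematomas may need drainage.

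On withdrawal, Section 6.5.1 lists implant removal or replacement among the reasons for which a woman may be withdrawn. It also asks that outcome data be collected on schedule if participation is discontinued. Section 6.4.2 combines the final visit with an early-withdrawal visit.

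**The concern.** The period of interest for short-term risk starts at surgery, and the duty to record starts at consent. For up to 14 days a woman can have an event on the plan's own list and recover from it without any sentence requiring that it be counted. Section 5.9 builds first-event Kaplan-Meier risks and person-year rates from these records, and does not say whether follow-up time starts at surgery or at consent. Missing early events push both estimates down, and a larger sample does not correct that. The direction matters because Section 13 expects safety similar to, or better than, the literature.

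A secondary point concerns the other end of follow-up. If data collection stops when an implant is removed or replaced, three planned analyses lose information: the recurrence risk by type of treatment (Section 5.5), the rates that count recurrences (Section 5.9) and the breast-level analyses (Section 5.9), in which the other breast is still at risk.

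**Working it through.** The plan states no figure for events before consent, so there is nothing to reproduce. The check is first textual, then an illustration of size.

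**Does any text reach back to surgery?**

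| Place | What it offers | Reaches back to surgery? |
|---|---|---|
| 5.5.1, recording duty | Form required for events after consent | No |
| 5.5.1, active inquiry | Period since the previous evaluation | Not stated; no study evaluation precedes Visit 1 |
| 6.4.1, Visit 1 tick | Adverse event evaluation | Period not stated |
| 6.4.2, Visit 1 procedures | History and examination | Not stated; finds events still present |
| 6.3, history | Eligibility questions, past diseases, medication | Not stated |
| Diary | Handed out at Visit 1 | No, prospective only |

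The gap is therefore limited to events that both begin and resolve before consent. By Section 5.3.1 it lasts up to 14 days, which is 14/60 = 23.3% of the time to the 60-day visit.

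**How large could the shortfall be?**

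Inputs: n = 350 per group (Section 5.10). Two quantities are assumptions, because the documents give neither: p, the true risk of an early complication, and f, the share of such events that begin and resolve before consent and go unrecorded.

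- Recorded risk = p × (1 − f).
- Shortfall = p × f.
- 95% half-width = 1.96 × √(p(1 − p)/350), a normal approximation with all 350 women observed. It is rough at small counts.

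For p = 2%: expected events = 350 × 0.02 = 7. Half-width = 1.96 × √(0.02 × 0.98/350) = 1.47 points.

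| f | Women unrecorded, of 7 | Recorded risk | Shortfall (points) |
|---|---|---|---|
| 25% | 1.75 | 1.5% | 0.5 |
| 50% | 3.5 | 1.0% | 1.0 |
| 75% | 5.25 | 0.5% | 1.5 |

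The shortfall passes the half-width when f exceeds 1.47/2 = 73%.

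For p = 5%: expected events = 17.5 and half-width = 2.28 points. At f = 25%, 50% and 75% the recorded risk is 3.75%, 2.5% and 1.25%. The shortfall passes the half-width when f exceeds 2.28/5 = 46%.

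For p = 1%: half-width = 1.04 points, which is larger than the risk itself, so no value of f takes the shortfall past it.

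**Follow-up after removal.** Two readings of Section 6.5.1 are open. In one, scheduled visits continue after discontinuation, because outcome data are to be collected on schedule. In the other, the early-withdrawal visit is the part of the schedule that applies, and follow-up ends there. The text does not choose. The second reading leaves the recurrence, rate and breast-level analyses without later data on these women.

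**The case against.** The best defence is that Section 5.5.1 sets a minimum and does not bar earlier events. Consent is signed at Visit 1, so the adverse event evaluation ticked there would be nearly empty unless it covered the time since surgery. The adverse event form asks for start date and duration. The expected events include malposition at the initial operation, and delayed healing is timed from implantation, so the authors evidently had the period from surgery in mind. Visit 1 also uses a surgical procedures form and a questions form whose contents are not shown. All this stands as a reason to expect that a careful site would capture some earlier events. It does not make capture required or uniform, and a risk estimate needs both.

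The missing Visit 1 line in Section 6.4.2 is weak evidence alone, because the visit table and the procedure lists differ elsewhere: questionnaires appear unticked at Visit 2 in the table but are applied there in the list. The point rests on the absence of any stated look-back. A reader might also infer something from the adverse event form not being among the Visit 1 forms, but that form is conditional and is on no visit's list.

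No text says that a hematoma is absorbed within 14 days, and some need drainage. That is a fair limit: the documents show that such events are plausible, not how common they are.

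A reader might infer that Section 6.5.1 contradicts itself. It does not have to: withdrawal is optional, the sentence naming an early termination visit stands in the paragraph on withdrawal of consent, and the schedule includes an early-withdrawal visit. The rule is unsettled. Nor does the number of expected removals measure lost events, since each explantation is itself to be investigated (Section 5.5).

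**Conclusion.** The concern holds in a limited form. Following Section 5.5.1 as written, an event that begins and resolves between surgery and consent need not be recorded, so early risks and rates can be biased downward. The size is unknown and rests wholly on assumed values of p and f. At 2% the shortfall exceeds the sampling half-width only if about three-quarters of such events are lost; at 5%, if about half are. Below that it is a one-sided error within the noise.

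A reader might infer that all complications of the first two weeks are lost, or that the safety alarms are undermined. The documents support neither. Events still present at Visit 1 can be recorded. The alarm events in Section 5.11 (contracture and the two kinds of removal) are little affected, since they are unlikely to come and go without trace before consent.

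Whether scheduled data collection continues after removal or replacement is an open question in the plan, secondary to the main point.

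**What to change.** 1. Amend Section 5.5.1 and the Visit 1 list in Section 6.4.2 so that, after consent, all events since implantation are recorded from the woman and her surgical record, dated from surgery and flagged as pre-consent. The list then agrees with the table in Section 6.4.1.
2. In Section 5.9, state implantation as time zero. Report short-term risk with the flagged events. Report it also without them, with each woman entering the risk set at her consent date (delayed entry), so that no event-free time is credited before enrolment.
3. State as a limitation that women not enrolled because of early complications remain unseen under either analysis.
4. Have the sponsor reconcile the withdrawal reasons, the data-collection sentence in Section 6.5.1 and the early-withdrawal visit in Section 6.4.2 with the analyses in Sections 5.5 and 5.9. This concerns study data collection only, and the choice is the sponsor's.

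Editorial clean-up only: the Visit 1 window (up to 14 days in Section 5.3.1; 14 days plus or minus 7 in one line of Section 6.4.2), the anchor for Visits 5 to 12 (inclusion in one place, implantation in another) and the unclear wording of exclusion criterion 9.

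Cost: a protocol amendment, a dated look-back section at Visit 1 and a short record review per woman. Pre-consent events will rest partly on recall, which is why they are flagged and reported both ways.
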